2. STUDY SYNOPSIS

Trial Title	Pharmacokinetic study of a novel lipid formulation of cannabidiol (CBD)
Short title	CLiP Study
Type of Study	CTIMP Pharmacokinetic study
Trial Design	Single-centre double-blind two-period crossover pharmacokinetic study
Planned Sample Size	14
Participants	Healthy volunteers
Eligibility Criteria	
Inclusion criteria
 
 i. Healthy volunteers. Defined as healthy on the basis of a clinical history, physical examination, ECG, vital signs, and laboratory tests of blood and urine. ii. Age 18-45 iii. Agreeing to fast 15 hours; 10pm-1pm on dosing days iv. Capable of giving informed consent v. Written informed consent from participant 
Exclusion criteria
 
 i. Clinically relevant medical history, physical findings, ECG, or laboratory values at the pre-trial screening assessment that could interfere with the objectives of the trial or the safety of the participant. ii. Presence of acute or chronic illness or history of chronic illness sufficient to invalidate the volunteer's participation in the trial or make it unnecessarily hazardous. iii. Impaired endocrine, thyroid, hepatic, respiratory or renal function, diabetes mellitus, coronary heart disease, or history of any neurological or mental illness. iv. Surgery or medical condition that might affect absorption of medicines. v. Blood pressure and heart rate in supine position at the screening examination outside the ranges: blood pressure 90–140 mm Hg systolic, 40–90 mm Hg diastolic; heart rate 40–100 beats/min. Repeat measurements are permitted if values are borderline (i.e. values that are within 5 mm Hg for blood pressure or 5 beats/min for heart rate) or if requested by the investigator. Subjects can be included if the repeat value is within range or still borderline but deemed not clinically significant by the investigator. vi. Loss of more than 400 mL blood during the 3 months before the trial, e.g. as a blood donor. vii. Any prescribed medication (apart from contraceptives) viii. Use of any CBD products within six months of IMP administration ix. Use of any over-the-counter medications or health supplements within the past 2 weeks x. BMI <18 or >30.0kg/m² xi. History of alcohol or substance misuse disorder xii. Intake of more than 14 units of alcohol weekly. xiii. Smokes more than 10 cigarettes per day xiv. Use of any illicit substances within the last six months of IMP administration xv. Pregnant or breastfeeding xvi. Women of childbearing potential (as defined in CTFG guidelines, see 5.7 Concomitant Medication) not willing to use a highly effective form of contraception (as defined in CTFG guidelines, see section 5.7 Concomitant Medication) during participation in the study or male

	
patients not willing to ensure use of a condom during participation in the study.
 
xvii. eGFR\leq 70 mls/min
 
xviii. Any liver function or renal function test abnormality. A repeat is allowed on one occasion for determination of eligibility.
 
xix. Urine drug screen positive for any substances
 
xx. Positive alcohol breath test
 
xxi. Participant in any other clinical trial or experimental drug study in the past 3 months
 
xxii. Known hypersensitivity to CBD and/or SEEK formulation excipients
 
xxiii. Participant is not able to swallow capsules
	
Study Drug	Cannabidiol (CBD) [GMP approved source]	
Formulation	
Novel lipid formulation (SEEK-CBD)
 
Standard formulation (STD-CBD)
	
Dose	1000mg	
Fed/fasting	Fasting	
Route of Administration	Oral	
Treatment Arms	SEEK-CBD then STD-CBD	
	STD-CBD then SEEK-CBD	
Treatment duration	One dose per experimental visit	
	Two experimental visits lasting 48 hours each	
Follow up duration	48 hours per dose/experiment	
	2 week washout between experiments	
	Final visit 7-14 days after second dosing session	
Planned Trial Duration	4 months	
Primary objective & outcome measure	To assess whether a novel lipid- formulation can improve the bioavailability of oral CBD in the fasting state.	AUC _{inf}
Secondary objectives & outcome measures	To characterise and compare the pharmacokinetic profiles of a novel CBD formulation and a standard formulation	C _{max} T _{max} AUC ₀₋₄₈ t _{1/2}

Pharmacokinetic Abbreviations

AUC _t	Area under the plasma concentration-time curve from time zero to time t.
------------------	--

AUC_{inf}	Area under the plasma concentration-time curve from time zero to time infinity.
Bioavailability	The proportion of drug absorbed into the systemic circulation
C_{max}	The maximum serum concentration that a drug achieves
C_{mean}	The mean serum concentration that a drug achieves over a specified period of time
CBD	Cannabidiol
CRF	Clinical Research Facility
GCP	Good Clinical Practice
GMP	Good Manufacturing Practice
King's CRF	NIHR Wellcome Kings Clinical Research Facility
KHPCTO	The King's Health Partners Clinical Trials Office
MHRA	Medicines and Healthcare products Regulatory Agency
REC	Research Ethics Committee
SLaM	South London and Maudsley NHS Foundation Trust
T_{max}	The time after administration of a drug that the C_{max} is observed
$T_{1/2}$	The time taken for the plasma concentration to fall by half its original value

3. BACKGROUND & RATIONALE

Cannabidiol (CBD) has been approved as a treatment for rare childhood epilepsies(1) and could be an effective treatment for psychotic disorders(2), anxiety disorders(3) and addictions(4). It is available as an oral liquid and as standard oral capsules.

The pharmacokinetics of CBD have been described in the review by Millar et al.(5). CBD is highly lipophilic and has poor oral bioavailability (around 5-10% in the fasted state). It also has very high protein binding capability (>97%) reducing the proportion of the drug which may cross the blood-brain barrier and have pharmacological activity in the brain(6). CBD also undergoes extensive first-pass metabolism in the liver by cytochrome P450 enzymes such as CYP3A4 and CYP2C19(7).

If taken with food, the absorption and bioavailability of CBD are much higher(5). In one study, a high-fat breakfast increased maximum plasma concentration (C_{max}) of CBD by 4.9x (90% CI 4.0–5.9) and area under the plasma concentration-time curve (AUC) by 4.2-fold (90% CI 3.6–4.9)(8). Other studies have similar results(9)(10). As a result of this food effect, when prescribing standard formulations of CBD, patients must carefully schedule their medication according to mealtimes. Otherwise, there may be large day-to-day variation in absorption, which will increase the risk of adverse effects or reduced efficacy.

One way to improve the bioavailability and reduce the food effect is by using a lipid encapsulation. Lipids enhance intestinal absorption by forming micelles, lipid molecules arranged in a spherical form in aqueous solutions. Around a third of CBD is absorbed into micelles(11). Once inside enterocytes, lipids are incorporated into chylomicrons, also known as ultra low-density lipoproteins. These are assembled in enterocytes using long-chain triglycerides, phospholipids, cholesterol and lipoproteins(12). Chylomicrons facilitate intestinal lymphatic transport, bypassing the portal vein (and avoiding first-pass metabolism)(13)(14). For most drugs, absorption through the lymphatic system is negligible, however, for highly lipid-soluble drugs such as CBD, passage into the intestinal lymphatic system may represent an alternative route of delivery into the general circulation(13). Preclinical

research using rats found that administering a lipid alongside CBD increased its peak concentration at mesenteric lymph nodes by 6x(15).

A few studies have examined the pharmacokinetics of novel formulations of CBD in humans, though most of these were at very low, sub-therapeutic doses(16). One study using CBD 25mg found that, compared to a medium-chain triglyceride formulation, a ‘novel self-emulsifying drug delivery system’ increased C_{max} by 4x and AUC by 2-3x(17). Another study using CBD 90mg showed that, compared to a powder formulation, a lipid formulation increased C_{max} by 22x and AUC by 7x (18). Finally, in a pilot study of a lipid formulation of CBD 10mg, the mean AUC was 7x higher compared to a standard formulation(19).

The formulation used in this study uses a range of fats that are designed to facilitate absorption by enterocytes in the ileum. The lipids that are all EU pharmacopoeia approved and have been used in medicinal products before. The effectiveness of the formulation has already been demonstrated with ibuprofen in the proprietary drug Flarin(20).

This study will compare the pharmacokinetics of this novel lipid formulation of CBD with the standard formulation. It will use a dose of 1000mg as this is the dose that is effective in patients with chronic psychotic disorders(2).

Scientific rationale for the choice of CBD dose

There have been two major clinical trials of CBD in patients with schizophrenia. (2)(21) McGuire et al. demonstrated efficacy at a dose of 1000mg/day CBD (Epidiolex in the fed state), while Boggs et al. found no beneficial effect at a lower dose of 600mg/day (in an alternative formulation). However, the current consensus is that these doses were relatively low, and that the optimal dose for treating schizophrenia is higher. Most evidence on the efficacy and safety of CBD is from epilepsy research. In a recent long-term open-label trial in children and adolescents with epilepsy (n=368, mean age 16 years, followed up for 3 years), participants were prescribed doses of CBD up to 30mg/kg/day (Epidiolex in the fed state).(22) After dose titration, the majority of participants were prescribed a daily dose greater than 20mg/kg/day, equivalent to 1400mg/day in a 70kg man. Because that study used Epidiolex in the fed state, the bioavailability is approximately equivalent to that with a 1000mg dose of the novel formulation (which mimics the effect of the fed state) in the study that we propose. In the epilepsy study by Patel et al., ‘doses above 20 mg/kg/day had acceptable tolerability, and no new safety issues emerged.’

We have selected a dose of 1000mg/day of the novel (formulation of CBD SEEK-CBD) for the proposed study because we plan to use this dose and formulation in subsequent clinical trials in patients with schizophrenia. This is therefore the appropriate dose for collecting pharmacokinetic data prior to its use in patients. Establishing its bioavailability empirically is particularly important, as CBD does not demonstrate dose-proportionality. (C_{max} slope 0.73; AUC_t slope 0.64).(Taylor et al. 2018)

A 7-fold increase in CBD exposure with 1000mg of SEEK-CBD would be dose equivalent to a 4-5 fold increase in exposure with 1500mg of regular CBD following a meal. In a study by Taylor et al (8), healthy volunteers received a single oral dose of conventional 1500 mg CBD in either the fed (high-fat breakfast) or fasted state. Food increased C_{max} by 4.85-fold (95% CI: 4.01–5.87) and AUC_t by 4.2-fold (90% CI 3.63–4.85). Critically, this study found that ‘there was no worsening in the severity of TEAEs in the fed state [compared to the unfed state], hence there is no appreciable safety concern’. Moreover, there were no serious adverse events: the most common were nausea, headache, and somnolence.

Several features of the proposed study's design will ensure the safety of the participants. The drugs will be administered in a state of the art NIHR Clinical Research Facility at King's College Hospital, which is purpose-built for pharmacokinetic studies of novel compounds. Adverse events will be monitored regularly, with medical staff will be on hand at all times. Participants will only leave the facility when all clinical and physiological measures are normal, and will be able to contact the investigators at any time after they leave. Participants will be able to remain in hospital overnight if required. The safety blood tests (LFTs, U&Es, FBC) are taken 4 hours post-dosing and the results will be available within 24 hours. If unexpected adverse events do arise, subsequent experimental sessions can be suspended and the study drug dose can be reduced. This contingency has been explicitly incorporated into the protocol (see section 9.5). We have also limited the maximum number of dosing sessions per day to three, so that action can be taken before multiple participants receive the study drug.

The gut microbiome and the endocannabinoid system

Commensal gut bacteria synthetise endocannabinoid precursors and influence the systemic availability of endocannabinoid agonists (e.g., anandamide).(23) This is important as endocannabinoids may mediate CBD's therapeutic effects.(24) This study will therefore complete a novel, exploratory analysis by comparing endocannabinoid levels within the two treatment arms to assess whether they are affected by the gut microbiome (ie. not between arms as the novel CBD should result in increased bioavailability, independent of the microbiome). The gut microbiome can also affect the activity of CYP3A4, a key enzyme involved in the breakdown of CBD.(25)

4. OBJECTIVES AND OUTCOME MEASURES

4.1 Primary objective

To assess whether the novel formulation is able to increase the bioavailability of oral CBD in the fasting state.

Hypothesis: the novel formulation will increase the AUC_{inf} for a single dose of oral CBD in the fasting state.

Primary outcome

Difference in AUC_{inf} for a single dose of oral CBD between the novel and standard formulations in the fasting state.

4.2 Secondary objectives

To characterise and compare the pharmacokinetic profiles of the novel CBD formulation and a standard formulation

Secondary outcomes

Differences between novel and standard formulations for:

- i. Maximum plasma concentration (C_{max})
- ii. Time after administration of drug when maximum plasma concentration is reached (T_{max})

- iii. Plasma half-life ($t_{1/2}$)
- iv. Area under the concentration-time curve from time zero to 48hours (AUC_{0-48})

4.3 Exploratory objective

To assess the effect of the gut microbiome on endocannabinoid and CBD metabolism. Outcomes are not pre-specified as this is an exploratory analysis.

4.4 TRIAL DESIGN

Single-centre double-blind two-period crossover pharmacokinetic study.

[figure not shown]
The study includes one baseline screening visit followed by two experimental visits each lasting 48 hours, separated by a minimum 2 weeks washout. Participants will return home each day and will not stay in the hospital overnight.

4.5 Trial Flow Chart

	Screening Visit Day -28 to day 0	Experimental visits 1 & 2*			Follow up visit 7-14 days after experiment 2 day 1
		Day 1	Day 2	Day 3	
Consent	X				
Demographic information	X				
Medical Assessment**	X				
Height, weight, body fat	X				
Eligibility Review	X	X			
Urine Pregnancy test	X	X			X
Urine Drug Screen	X	X			
Alcohol breath test	X	X			
Fasting		X			
Drug Administration		X			
Intravenous Cannulation		X			
Blood sampling (FBC, LFTS, U&Es)	X	X			
Blood sampling (CBD and metabolites)		X	X	X	X
Urinalysis	X	X			
Vital Signs	X	X	X	X	
Drug Effects Questionnaire (DEQ-5)		X	X	X	
Gastrointestinal Symptom Rating Scale		X	X	X	
Stool Sample Kits	X				
Adverse events		X	X	X	X
Washout period*				X	

*Minimum 2 weeks between experimental visits

**Includes physical exam, vital signs, urine drug screen, alcohol breath test, blood test (U&Es, LFTs, FBC)

5. TRIAL MEDICATION

5.1 Study Drug

The study drug is cannabidiol, a naturally occurring phytocannabinoid with minimal adverse effects. CBD oral solution is an approved treatment for rare childhood epilepsy syndromes.

The trial will use two formulations of CBD:

1. CBD standard formulation (STD-CBD)
2. CBD novel lipid formulation (SEEK-CBD).

Participants will be administered the same total dose of CBD in both arms (1000mg). Both STD-CBD and SEEK-CBD capsules contain 200mg CBD. Participants will therefore be administered 5x 200mg capsules.

The study drug will be provided by SEEK pharmaceuticals. The trial will use the same source of CBD for both arms.

The two formulations will have an identical appearance so that participants cannot tell which formulation they have been administered.

5.2 Risks, known drug reactions and interaction with other therapies

The risks associated with the study are minimal. CBD has few adverse effects. A meta-analysis of randomized controlled clinical trials found that when prescribed alone, diarrhoea was the only adverse effect (26). CBD also has pharmacokinetic interactions with other medicines via hepatic CYP enzymes, but these are highly unlikely to be relevant to this study as concomitant medications (apart from contraceptives) are prohibited. Previous studies have tested oral doses of CBD (Epidiolex) as high as 4500mg and 6000mg without severe or serious adverse events(8) (27).

The BNF recommends that clinicians should avoid prescribing enzyme-inducing drugs alongside contraceptive medications. CBD is a potent inhibitor of CYP2C19 and CYP3A4 and is not known to have any other clinically relevant enzyme interactions(6).

CBD is not known to cause drug reactions.

5.3 Formulation

SEEK pharmaceuticals will provide both formulations.

The novel SEEK-CBD formulation contains the following excipients:

- Gelucire 43/01 (glycerides only; hard fat [EP]), manufactured by Gattefosse
- Maisine CC (glyceryl monolinoleate), manufactured by Gattefosse
- PEG 400 (polyethylene glycol 400)

Each 200mg CBD capsule contains 400mg Gelucire 43/01, 200mg Maisine CC and 0.008mls PEG 400. The Maisine CC, Gellucire 43/01 and PEG400 are mixed with heating in a closed vessel to 50°C degrees. CBD is added in a single portion and is stirred at 50°C for 30 minutes. The mixture is cooled to approximately 40°C and then filled into the hard gelatin capsules. The top part of the capsule is replaced and the filled capped capsules are left to stand at room temperature until solidified. The capsules are then stored in a plastic bag. All excipients are GMP approved. The materials used in the manufacture of the capsules is of plant origin.

5.4 Drug storage and supply

The investigational product will be purchased from the manufacturer free of charge. It will be stored below 25°C in the Maudsley Pharmacy. At the end of the study, any unused study drug will either be returned to the manufacturer or will be destroyed by the Maudsley Pharmacy according to standard local procedures.

5.5 Preparation of Investigational Medicinal Product

The study drug will be manufactured by Eurofins. It will be sent to IPS Pharma who will add the Annex 13 labels. IPS Pharma will complete the final Qualified Person (QP) release. The labels will have been approved by Maudsley Pharmacy. The study drug will dispensed by the Maudsley pharmacy according to standard procedures.

5.6 Dosing, Compliance & Drug Accountability

Participants will be administered a dose of CBD 1000mg on each experimental visit. There will be a minimum of 2 weeks washout between study drug administrations (i.e. between day 1 of each experiment). There is no maximum timeframe between doses. Eligibility for the study will be reassessed on Day 1 of experimental visit 2.

There are not expected to be any issues with either compliance or drug accountability. Full IMP accountability will be maintained. If medication is dispensed by the Maudsley Pharmacy but is not administered (for example, if a participant withdraws from the study during an experimental visit) the drug will be returned to the Maudsley Pharmacy to be disposed of according to standard local procedures.

5.7 Concomitant Medication

Apart from contraceptives, concomitant medications are not permitted during the study and are an exclusion criterion.

There is inadequate information on the effects of cannabidiol on the foetus. Female participants of child-bearing potential* should use a highly effective method of contraception** for the duration of the trial and for 4 weeks after the completion of the trial.

*A woman is considered of childbearing potential (WOCBP), i.e. fertile, following menarche and until becoming post-menopausal unless permanently sterile. Permanent sterilisation methods include hysterectomy, bilateral salpingectomy and bilateral oophorectomy. A postmenopausal state is defined as no menses for 12 months without an alternative medical cause. A high follicle stimulating hormone

(FSH) level in the postmenopausal range may be used to confirm a postmenopausal state in women not using hormonal contraception or hormonal replacement therapy. However in the absence of 12 months of amenorrhea, a single FSH measurement is insufficient.

** Methods that can achieve a failure rate of less than 1% per year when used consistently and correctly are considered as highly effective birth control methods. Such methods include:

- combined (oestrogen and progestogen containing) hormonal contraception associated with inhibition of ovulation:
 - oral
 - intravaginal
 - transdermal
- progestogen-only hormonal contraception associated with inhibition of ovulation:
 - oral
 - injectable
 - implantable
- intrauterine device (IUD)
- intrauterine hormone-releasing system (IUS)
- bilateral tubal occlusion
- vasectomised partner
- sexual abstinence (abstinence should only be used as a contraceptive method if it is in line with the subjects' usual and preferred lifestyle. Periodic abstinence (calendar, symptothermal, post-ovulation methods) is not an acceptable method of contraception)

Males participants must be willing to use a condom throughout the duration of the study.

6. SELECTION AND WITHDRAWAL OF PARTICIPANTS

6.1 Inclusion criteria

- Healthy volunteers. Defined as healthy on the basis of a clinical history, physical examination, ECG, vital signs, and laboratory tests of blood and urine.
- Age 18-45
- Agreeing to fast 15 hours; 10pm-1pm on dosing days
- Capable of giving informed consent
- Written informed consent from participant

6.2 Exclusion criteria

- i. Clinically relevant medical history, physical findings, ECG, or laboratory values at the pre-trial screening assessment that could interfere with the objectives of the trial or the safety of the participant.
- ii. Presence of acute or chronic illness or history of chronic illness sufficient to invalidate the volunteer's participation in the trial or make it unnecessarily hazardous.
- iii. Impaired endocrine, thyroid, hepatic, respiratory or renal function, diabetes mellitus, coronary heart disease, or history of any neurological or mental illness.
- iv. Surgery or medical condition that might affect absorption of medicines.
- v. Blood pressure and heart rate in supine position at the screening examination outside the ranges: blood pressure 90–140 mm Hg systolic, 40–90 mm Hg diastolic; heart rate 40–100 beats/min. Repeat measurements are permitted if values are borderline (i.e. values that are within 5 mm Hg for blood pressure or 5 beats/min for heart rate) or if requested by the investigator. Subjects can be included if the repeat value is within range or still borderline but deemed not clinically significant by the investigator.
- vi. Loss of more than 400 mL blood during the 3 months before the trial, e.g. as a blood donor.
- vii. Any prescribed medication (apart from contraceptives)
- viii. Use of any CBD products within six months of IMP administration
- ix. Use of any over-the-counter medications or health supplements within the past 2 weeks
- x. $BMI <18$ or $>30.0\text{kg}/\text{m}^2$
- xi. History of alcohol or substance misuse disorder
- xii. Intake of more than 14 units of alcohol weekly.
- xiii. Smokes more than 10 cigarettes per day
- xiv. Use of any illicit substances within the last six months
- xv. Pregnant or breastfeeding
- xvi. Women of childbearing potential (as defined in CTFG guidelines, see 5.7 Concomitant Medication) not willing to use a highly effective form of contraception (as defined in CTFG guidelines, see section 5.7 Concomitant Medication) during participation in the study or male patients not willing to ensure use of a condom during participation in the study.
- xvii. $eGFR \leq 70 \text{ mls}/\text{min}$
- xviii. Any liver function or renal function test abnormality. A repeat is allowed on one occasion for determination of eligibility.
- xix. Urine drug screen positive for any substances
- xx. Positive alcohol breath test
- xxi. Participant in any other clinical trial or experimental drug study in the past 3 months
- xxii. Known hypersensitivity to CBD and/or SEEK formulation excipients
- xxiii. Participant is not able to swallow capsules

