6.4 Payment

Participants will be reimbursed for their time at a rate equivalent to £10.55/hour. The total time commitment for each participant is 34 hours. The payment to participants on successful completion of the whole study will be £360. It is essential that participants attend on time for all blood tests across both experiments, therefore, participants will only be paid on successful completion of all aspects of the study. If a participant completes the baseline visit but does not complete experimental visits they will be paid £40. If a participant successfully completes the optional stool sampling assessments they will receive an additional £20. The total potential reimbursement is therefore £380.

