7.7.3 Experimental Visit

7.7.3.1 Day 1

The following interventions and assessments will be completed in order:

- i. Fasting (previous night from 10pm)
- ii. Eligibility review
- iii. Urine sample for pregnancy and illicit drugs testing

- iv. Alcohol breath test
- v. GSRS
- vi. Intravenous cannulation
- vii. Pre dose; 0-5mins: blood sampling; vital signs; DEQ-5
- viii. 0 mins: drug administration
- ix. 30mins: blood sampling
- x. 1 hour: blood sampling; vital signs; DEQ-5
- xi. 2 hours: blood sampling; vital signs; DEQ-5
- xii. 3 hours: blood sampling
- xiii. 4 hours: blood sampling; vital signs; DEQ-5; urinalysis
- xiv. 5 hours: blood sampling
- xv. 6 hours: blood sampling
- xvi. 8 hours: blood sampling; vital signs; DEQ-5; adverse events assessment

7.7.3.1 Day 2

- i. 24 hours post dose: blood sampling; vital signs; DEQ-5; GSRS; adverse events assessment

7.7.3.1 Day 3

- i. 48 hours post dose: blood sampling; vital signs; DEQ-5; GSRS; adverse events assessment.
- ii. Payment via bank transfer (if final visit)
- iii. Book follow-up visit (if final visit) and provide a urine pregnancy test (if female)

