7.7.5 Follow-up visit

The follow-up visit will be completed via remote video call 7-14 days after day 1 of experiment 2. Participants will be asked to report adverse events. Female participants of childbearing potential will be asked to confirm the result of a urine pregnancy test completed on that day.

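### Exclusion xvi screens women for contraception during participation only and omits the 4 weeks after completion that section 5.7 requires (minor safety inconsistency)

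*Protocol*

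**What the plan says.** Protocol section 5.7 (Concomitant Medication) gives the reason for the precaution: "There is inadequate information on the effects of cannabidiol on the foetus". It then states that women of childbearing potential "should use a highly effective method of contraception", and gives the period as "for the duration of the trial and for 4 weeks after the completion of the trial".

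Exclusion xvi in section 6.2, with the same wording in the synopsis, turns this into an entry test of willingness. The women's part ends "see section 5.7 Concomitant Medication) during participation in the study". No later period is named.

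For men, section 5.7 reads "Males participants must be willing to use a condom throughout the duration of the study". Exclusion xvi also limits their condom use to the time of participation, so the two places agree.

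On timing, section 7.7.5 says "The follow-up visit will be completed via remote video call 7-14 days after day 1 of experiment 2". Section 6.11 defines the end of the trial as database lock. Neither document says when the trial is complete for an individual participant. The SAP does not mention contraception.

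**The concern.** An entry criterion should screen for the whole of a safety precaution that the protocol sets elsewhere. Here the two sections give different periods. A screener who applies xvi literally would accept a woman who is willing to use contraception while she takes part but says she will stop as soon as she has finished.

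The 4 weeks fall mostly or wholly after the last scheduled contact, so willingness at entry is the practical place to secure them. Two periods in one protocol also invite inconsistent screening and counselling. What is at stake is a foetal-safety precaution in a small group of healthy volunteers. No estimate or test in the trial depends on it.

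**Working it through.** The plan gives no figure to reproduce. The check compares the texts and then asks whether the gap has a definite length.

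**1. Do the pointers in xvi bring in the 4 weeks?** Exclusion xvi refers to 5.7 twice. Each reference sits in a parenthesis about a definition: the first defines childbearing potential, the second defines a highly effective method. The period follows outside the parenthesis, in xvi's own words. The pointers therefore import definitions, not duration.

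**2. Is women's willingness tested elsewhere?** For women, 5.7 is worded as conduct ("should use a highly effective method of contraception"). For men, it is worded as willingness ("Males participants must be willing to use a condom throughout the duration of the study"). Read literally, xvi is the only place that tests a woman's willingness.

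**3. Does anything else cover the 4 weeks?** The other criteria in 6.1 and 6.2, the withdrawal criteria in 6.10, the flow chart in 4.5 and the visit lists in 7.7 do not mention them. The last scheduled contact is the follow-up call, with a pregnancy test that day.

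**4. How long is the gap?** Count days from the second dose and take 4 weeks as 28 days. Then gap = (day of completion + 28) − (day participation ends). The follow-up call is on day 7 to 14 (section 7.7.5). Day 3 of the second experimental visit is 48 hours after the dose, so day 2. Day 3 is a candidate because payment is scheduled there, and section 6.4 says "participants will only be paid on successful completion of all aspects of the study".

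| Participation ends | Completion means | 5.7 runs to | Gap |
|---|---|---|---|
| Call | Call | 7 + 28 = 35 to 14 + 28 = 42 | 28 days |
| Day 3 | Day 3 | 2 + 28 = 30 | 30 − 2 = 28 days |
| Call | Day 3 | 30 | 30 − 14 = 16 to 30 − 7 = 23 days |
| Day 3 | Call | 35 to 42 | 35 − 2 = 33 to 42 − 2 = 40 days |
| Either | Database lock | Lock + 28 | Not computable; lock date not given |

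The rows disagree and the last has no number, so no day range is offered as the size of the problem. What the rows share is that the gap is never zero.

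**5. Could moving the anchor in 5.7 shorten the precaution?** Yes, on one reading. If completion means the end of the trial as 6.11 defines it, 5.7 runs to database lock plus 28 days. Section 7.8 schedules the laboratory analyses after all samples have been collected, so lock would be expected to follow a participant's own call. Anchoring 5.7 to that call would end the period earlier, on day 35 to 42.

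**The case against.** The strongest reply is that the practical effect is slight. Exclusion xvi sends the reader to 5.7 twice, and the 4 weeks stand there in the same sentence that carries the definition markers. Section 5.7 binds enrolled women whatever xvi says. Pregnancy is tested at screening, on both dosing days and at follow-up, and section 9.1 makes any unplanned pregnancy reportable. The contrast between conduct and willingness wording may be no more than loose drafting. Whether women are told of the 4 weeks, and agree to them, depends largely on the participant information and consent form, which were not available for this review.

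Most of this stands, and it is why the point is minor. It does not remove the mismatch: the tests stop at the follow-up call, and the willingness test stops at participation.

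The Day 3 reading of completion is also open to challenge. The synopsis places the final visit 7 to 14 days after the second dosing session, and the Day 3 list itself includes booking the follow-up visit. Setting that reading aside changes the possible lengths of the gap but not its existence.

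A reader might infer more than the documents support:

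- **That the 4-week precaution is missing from the protocol.** It is not; it stands in 5.7.
- **That a definite number of days is uncovered.** The end points are not defined well enough to say.
- **That 5.7 should simply be re-anchored to the follow-up visit.** That could shorten the precaution on a literal database-lock reading.
- **That the men's rule has the same fault.** Its two statements agree.

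**Conclusion.** The inconsistency is real in the current text and minor. Exclusion xvi tests women's willingness for a shorter period than 5.7 requires, and no other criterion or scheduled contact makes up the difference. The defect lies in the entry criterion, not in the precaution itself.

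It matters only for a woman who is willing during participation but not for the weeks after it. The documents do not allow that number to be derived; planned recruitment is 14 in total. The conclusion rests on reading xvi's pointers as attached to definitions. It does not depend on which end point completion means. The primary analysis, power and sample size are unaffected.

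**What to change.** In the women's part of exclusion xvi, in both section 6.2 and the synopsis, add after the reference to participation: *and for the 4 weeks after completion required by section 5.7*. The men's part needs no change.

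Leave the requirement in 5.7 in place. Ask the sponsor to confirm which participant-level end point completion means, for example the follow-up visit. That choice should be made openly, because any such end point would be shorter than a literal database-lock reading. Check that the participant information states the same period.

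The cost is a one-line edit in two places, one clarification from the sponsor and the check of the participant information. An occasional volunteer may decline.
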